9.6 Early Treatment Termination

Subjects that terminate IP treatment prior to completing the planned treatment portion of the protocol will have an early termination visit within 30 days of ending the treatment portion of the study. Subjects will have a termination visit with the following procedures completed:

- Vital signs
- Review concurrent meds
- Assess for any Adverse Events
- Skin exam limited to all target lesions
- Photograph and measure Target lesions
- Complete bloodwork (CBC, CMP)
- Complete subject payment form

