9.4 Study Assessments

9.4.1 Tumor Measurements:

Tumor measurements will be done at each visit. Imaging assessment with high frequency ultrasound will be done at baseline and at the second follow-up visit (Visit 6). At baseline, up to 5 TILs that are at least 10cm apart will be selected to be followed over the course of the study. Up to 10 TNILs can be followed with no more than 2 TNILs selected in the same anatomical area as a TIL. Responses in TILs and TNILs will be measured serially. Clinical measurements will be performed with a millimeter measuring tape (Appendix A). All measurements will be selected that will be able to be followed clinically and for ultrasound evaluations. The RECIST 1.1 (Appendix B) response criteria will be used to evaluate tumor response. Individual tumor measurements will also be conducted to determine clinical management of TILs and TNILs. The timeframe for the clinical (primary endpoint) and evaluation will be at Visit 6 and for high-frequency ultrasound (secondary endpoints) at Visit 6 as well.

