9.5 End of IP treatment

Subjects that complete the planned treatment portion of the study will have move into the follow up period.

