15. REMOVAL OF SUBJECTS

Subjects have the right to withdraw from the study at any time and for any reason without prejudice to their future medical care by the provider or at the institution. If this occurs, the investigator, or designee, is to discuss with the subject the safe and appropriate processes for discontinuation from the investigational product, intervention or device.

Subjects that wish to discontinue active IP treatment/intervention/device may elect to continue with the other protocol required assessments. The investigator should discuss with the subject the options for continuation of the study schedule of assessments (i.e. blood work, scans, physical exams, diaries) and collection of data, including endpoints and adverse events.

The investigator or designee must document the change in status of the subject's participation in the study and as applicable, the level of follow up that is agreed to by the subject (i.e. agrees to follow up exams, adverse event review, phone contact, but not to further treatment and/or procedures).

Subject withdrawal of consent for a study indicates that the subject does not wish to receive further protocol required therapies or procedures, and the subject does not wish to, or is unable to continue further study participation. Subject data only up to the time when consent is withdrawn will be included in the analysis of the study.

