16.2 Statistical Analysis

Any patient who was treated with at least 1 dose of talimogene laherparepvec therapy will be included in safety and efficacy analysis. Descriptive statistics (mean, median, standard deviation, 25th percentile, 75th percentile, and range) will be presented for continuous variables, such as age. Frequency counts will be presented for categorical variables such as sex and race.

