16.2.1 Overall Response Rate (ORR)

The analysis of ORR will use a Simon two-stage optimum design to test that the proportion with ORR is \geq 80% (alternative hypothesis) versus ORR \leq 50% (null hypothesis). In the first stage, 7 patients will be recruited. If \leq 4 have ORR the trial will be terminated. If 5 or more have ORR, accrual will continue to the second stage. In the second stage, an additional 13 patients will be recruited. At the end of the second stage, if \geq 14 patients have ORR then TVEC will be considered promising for further study. This design yields 80% statistical power with a one-sided alpha level of 0.05.

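### Subjects who stop injections early stay in the efficacy analysis but are not required to have the Visit 6 reading on which response depends, which puts a thin power margin at risk

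*Combined protocol and SAP*

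**What the plan says.** The primary reading is tied to one visit. Section 9.4.1 states: "The timeframe for the clinical (primary endpoint) and evaluation will be at Visit 6". Section 9.4.1.1 requires both CR and PR to be confirmed there, 8 weeks after the end of the injections.

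Who is scheduled for that visit depends on how treatment ends:

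- Section 9.5, for completers: "Subjects that complete the planned treatment portion of the study will have move into the follow up period".
- Section 9.6, for everyone else: "Subjects that terminate IP treatment prior to completing the planned treatment portion of the protocol will have an early termination visit within 30 days". Lesions are measured at this visit. It closes with the subject payment form, which otherwise appears only at Visit 8.
- Section 15 says that subjects who wish to stop treatment "may elect to continue with the other protocol required assessments", and asks the investigator to discuss this with them.
- Section 9.8 lists treatment, early termination and follow-up visits together as what must be finished before a subject is off study. It does not assign them to groups of subjects.

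The analysis set does not depend on any of this. Section 16.2 states: "Any patient who was treated with at least 1 dose of talimogene laherparepvec therapy will be included in safety and efficacy analysis". Sections 16.2.1 and 16.3 apply fixed counts of 7 and 20 subjects. They do not say how a treated subject without Visit 6 is scored, and they make no allowance for dropout.

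**The concern.** The plan keeps early stoppers in the denominator but does not require the assessment that decides whether they enter the numerator.

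The protocol itself foresees stopping for reasons other than tumour growth. Section 8.3 takes a subject off treatment after a related-event delay of more than 6 weeks. Section 11.4 lists persistent discomfort and a newly found high-risk feature. Section 8.5 covers ongoing antiviral treatment. Such a subject may be responding. If the response is never confirmed at Visit 6, the subject counts as a failure, and the estimated ORR moves down for a reason unrelated to the drug's activity. With 7 subjects in stage 1, one such case can decide whether the trial continues.

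The routing is also open to different readings, so the two sites could handle the same kind of subject differently.

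**Working it through.** **Timing.** Visit 6 is 28 + 28 = 56 days after Visit 4. At the short end of both visit windows it is 21 + 21 = 42 days. A termination visit within 30 days of the last injection falls before either, so it cannot be the 8-week confirmation.

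**Design inputs (16.2.1).** The null rate is 0.50 and the alternative 0.80, with 7 subjects in stage 1 and 13 in stage 2. The stage 1 rule, quoted here without the at-most sign before its first number, is: "4 have ORR the trial will be terminated. If 5 or more have ORR, accrual will continue to the second stage". Success is 14 or more responders of 20. The stated power is 80% at one-sided alpha 0.05.

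**Reproducing the plan's figure.** With response probability p,

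Pr(success) = Σ over x = 5, 6, 7 of Pr[Bin(7, p) = x] × Pr[Bin(13, p) ≥ 14 − x].

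At p = 0.80:

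| x | Pr[Bin(7) = x] | Pr[Bin(13) ≥ 14 − x] | product |
|---|---|---|---|
| 5 | 0.2753 | 0.9009 | 0.2480 |
| 6 | 0.3670 | 0.9700 | 0.3560 |
| 7 | 0.2097 | 0.9930 | 0.2083 |

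The sum is 0.812, so the stated 80% reproduces, with 1.2 points to spare. At p = 0.50 the same sum is 0.0417, within the 0.05 limit. The chance of stopping at stage 1 when p = 0.80 is 0.148.

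**Sensitivity by rate.** The documents give no early-stopping rate, so the share d is an assumption. Suppose a share d of treated subjects has no Visit 6, counts as non-responders, and stops independently of response. Then p becomes 0.80 × (1 − d), with the bounds unchanged.

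| d (assumed) | p | power | stop at stage 1 |
|---|---|---|---|
| 0% | 0.800 | 0.812 | 0.148 |
| 1% | 0.792 | 0.791 | 0.162 |
| 5% | 0.760 | 0.696 | 0.223 |
| 10% | 0.720 | 0.561 | 0.308 |

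**Sensitivity by count, without assuming a rate.** Fix exactly one subject as an unscored failure and let the others respond at 0.80.

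- In stage 1, at least 5 of the other 6 must respond: 0.3932 × 0.9009 + 0.2621 × 0.9700 = 0.61. Stopping at stage 1 has probability 1 − (0.3932 + 0.2621) = 0.345.
- In stage 2, the second factor uses 12 subjects instead of 13: 0.2753 × 0.7946 + 0.3670 × 0.9274 + 0.2097 × 0.9806 = 0.76.

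**When nothing is lost.** If stoppers are followed to Visit 6 and respond at 0.80, p stays at 0.80 and power at 0.812. The same holds if the 80% alternative was set as an all-treated rate that already counts such subjects as failures. The documents do not say whether it was.

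**The case against.** The strongest reply is that the protocol separates stopping treatment from leaving the study. Section 9.6 adds a visit without saying that it replaces follow-up. Section 9.8 lists follow-up visits before a subject is off study. Section 15 lets subjects continue and mentions endpoint data. Sections 8.3 and 11.4 speak of stopping treatment only. This stands as far as it goes: a reader might infer that early stoppers never reach Visit 6, and the documents do not support that. But continuation under Section 15 is optional and worded for subjects who themselves wish to stop, and 9.5 names only completers. Visit 6 is permitted for these subjects, not required.

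Four further points stand.

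- A reader might infer that subjects whose lesions all clear before the fourth injection also lose Visit 6. Table 7 says otherwise: cleared lesions get no further injections and are followed for 6 months.
- Not every early stopper is unscorable. A sole injected lesion withdrawn for confirmed progression is PD under Appendix B, a non-response with or without Visit 6.
- Sections 16.1.1 and 16.2 together already imply that a treated subject without confirmed response is in the denominator and not the numerator. An explicit rule is a clarification, and dropping such subjects would depart from 16.2.
- Any error is conservative for a false positive: at d = 10% the type I error falls from 0.0417 to 0.0152.

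One timing caveat also applies. Section 9.6 counts its 30 days from the end of the treatment portion, which it does not define. If that means the date of the decision to stop, a subject removed under 8.3 would already be at least 2 + 6 = 8 weeks past the last injection, and the termination visit could fall after the 8-week mark. No section says that this visit may stand in for Visit 6, so the routing still needs reconciling. Stops under 11.4 need not involve such a delay.

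**Conclusion.** The gap is real but narrower than it may first appear. Subjects taken off injections without documented progression remain in the efficacy analysis, yet no section requires them to have the reading that confirms response. A responder among them who does not attend Visit 6 would count as a failure.

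A reader might conclude that the stated power is lost. The documents do not show that. The 80% figure is correct for the design as written. The loss depends on a rate that the plan does not give, on the stoppers actually missing Visit 6, on stopping being independent of response, and on the 80% alternative not already including them. Under those assumptions power is 0.79, 0.70 or 0.56 at 1%, 5% or 10%. A single such subject takes it to 0.61 if in stage 1 and 0.76 if in stage 2. Power is at risk because the margin is about 1 point and the stages are small.

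This should be corrected, since it touches the primary endpoint and the stage 1 decision and the remedy uses visits that already exist.

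**What to change.** - Reconcile 9.5 and 9.6 with 9.8, Section 15 and Table 7. Subjects who stop injections without withdrawing consent should stay by default on the existing lesion assessments, at least through Visit 6. Reserve the early termination visit for subjects leaving the study.
- In 16.2.1 and 16.3, state that a treated subject with no Visit 6 assessment counts as a non-responder at both stages. This keeps the 7 and 20 denominators intact. It does not restore power by itself; the attendance change does that.
- State in 16.2.1 whether the 80% alternative already counts such subjects as failures.

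The cost is a short amendment and a few already defined visits for a small number of subjects. No treatment rule changes. Subjects who withdraw consent or decline to attend will still lack Visit 6, and the scoring rule covers them.

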8.5 Definition of a Dose Limiting Toxicity (DLT)

Definitions of dose-limiting toxicity:

Toxicity will be evaluated according to CTCAE version 4.0. DLT will be defined as any of the following talimogene laherparepvec-related toxicity during treatment and up to 30 days after end of treatment.

The following herpetic events should be considered as DLTs:

- Serious herpetic events such as herpetic encephalitis, encephalomyelitis or disseminated herpetic infection.
- Any herpetic events (with the exclusion of oral and genital outbreaks) that are at least possibly due to talimogene laherparepvec and require treatment with acyclovir or similar anti-viral agent. Talimogene laherparepvec treatment should be suspended if treatment is required with systemic acyclovir or other anti-virals. If ongoing anti-viral treatment is required, talimogene laherparepvec treatment should be permanently discontinued.

Consider also including the following as DLTs:

- Grade 3 or greater immune-mediated adverse events.
- Any grade plasmacytoma at or near the injection site or evidence of impaired wound healing at the injection site.
- Grade 3 or greater allergic reactions considered at least possibly related to talimogene laherparepvec.
- Grade 4 non-hematologic toxicity.
- Grade 3 non-hematologic toxicity lasting > 3 days despite optimal supportive care;
 - Grade 3 fatigue will not be classified as DLT, irrespective of duration.
- Any Grade 3 or higher non-hematologic laboratory value if:
 - medical intervention is required, or
 - o the abnormality leads to hospitalization, or
 - the abnormality persists for > 1 week unless deemed not clinically important per both investigator and sponsor.
- Grade 3 or 4 febrile neutropenia.

- Grade 4 thrombocytopenia associated with bleeding event requiring intervention.
- Any other intolerable toxicity leading to permanent discontinuation of talimogene laherparepvec.
- Grade 5 toxicity (ie. death).

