9.5.1 Follow up

Visit 5- First follow up visit (28 +/- 7 days)

- Vital signs
- Review con meds
- Assess for any Adverse Events
- Skin exam limited to all target lesions
- Photograph and measure target lesions (Appendix A)
- Schedule the next follow up visit in 4 weeks.

Visit 6- Second follow up visit (28 +/- 7 days)

- Vital signs
- Review con meds
- Assess for any Adverse Events
- Skin exam limited to all target lesions
- Photograph and measure target lesions (Appendix A)
- Schedule second ultrasound to be completed on TILs before next follow up visit
- Schedule the next follow up visit in 6 weeks.

Visit 7- Third follow up visit (42 +/- 10 days)

- Vital signs
- Review concurrent meds

- Assess for any Adverse Events
- Skin exam limited to all target lesions
- Photograph and measure target lesions (Appendix A)
- Schedule the next follow up visit in 14 weeks.

Visit 8 - Fourth follow up visit (98 +/- 21 days)

- Vital signs
- Review con meds
- Assess for any adverse events
- Skin exam limited to all target lesions
- If sites are free of disease, participant participation will be complete
- Photograph and measure target lesions (Appendix A)
- Complete subject payment form

Visit 9 – Telephone Follow up (356 +/- 31 days) after Visit 1

• Assess for changes of target lesions

• If active lesion(s) are noted by the participant, they will follow up with a dermatologist and their records will be requested

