9.8 Off Study

Subjects will be considered off study when all planned treatment, early termination and follow-up visits have been completed, unless death or withdrawal of consent to continue participation occurs.

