11.4 Process to implement study closure when significant risks or benefits are identified

The PI will be advised of all study related AEs and will determine if the study at a certain point may need to be closed due the AEs.

Study stopping criteria will include the following:

- Death within 30 days after the investigational treatment at least possibly related to the study treatment.
- Any herpetic event or complication requiring hospitalization that is at least possibly related to the investigational agent within 30 days to treatment.

Individual treatment stopping criteria will include the following:

- 75% or greater number of TILs meeting criteria for withdrawal.
- Identification of high-risk feature in one or more TILs during study participation.
- Persistent discomfort (consecutive weeks of lesion pain, burning, or itching of Grade 2 or more).

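### The early termination visit has a latest day but no earliest day, so a subject who stops early can have the last required AE assessment before the 30-day DLT and study stopping windows close

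*Combined protocol and SAP*

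**What the plan says.** **Early termination visit (9.6).** A subject who stops before finishing planned treatment "will have an early termination visit within 30 days of ending the treatment portion of the study". No earliest day is given. The listed procedures include an AE assessment and end with the payment form. No further contact is scheduled. In 9.5.1 and 9.6 the payment form appears only here and at Visit 8, the last clinic visit for completers.

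**Windows that run to 30 days.** Section 8.5 counts as a DLT any qualifying treatment-related "toxicity during treatment and up to 30 days after end of treatment". Section 11.4 has two study stopping criteria: "Death within 30 days after the investigational treatment at least possibly related to the study treatment" and "Any herpetic event or complication requiring hospitalization that is at least possibly related to the investigational agent within 30 days to treatment".

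**Who is followed afterwards.** Section 9.5: "Subjects that complete the planned treatment portion of the study will have move into the follow up period". Section 9.8: "Subjects will be considered off study when all planned treatment, early termination and follow-up visits have been completed", with exceptions for death and withdrawal of consent. Section 15 says that a subject who wishes to stop the product "may elect to continue with the other protocol required assessments". Table 7 withdraws a subject whose only injected lesion has confirmed progression.

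**AE schedule (Section 26).** AE evaluation is marked for Visits 1 to 8 and for the early termination visit. It is not marked for the 12-month telephone contact, which covers changes in target lesions only.

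**The concern.** A window that closes on day 30 cannot be relied on to be observed by a visit that may be held on any day from 0 to 30. Only a visit on the last permitted day covers it, if visit and window are counted from the same date. The visit also reads as terminal for an early stopper: it schedules nothing, and the follow-up period is described only for completers.

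Two things are at stake:

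- **Safety endpoint.** AE, grade 3 or higher AE and SAE incidence (16.1.2) would rest on unequal periods of active ascertainment. Completers are assessed up to Visit 8, nominally 28 + 28 + 42 + 98 = 196 days after the last injection. An early stopper's active assessment may end within days of the last dose.
- **Study stopping criteria.** A related death, or a herpetic event with hospitalisation, could fall inside the 30 days but after the last required contact. It would then reach the study only if someone reported it.

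**Working it through.** The plan states no figure for this point, so there is none to reproduce. The check is visit-window arithmetic.

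**Inputs**

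- Visit 1 to 2: 21 ± 3 days; Visit 2 to 3 and Visit 3 to 4: 14 ± 3 days each (9.3, 9.7).
- Visit 4 to 5 and Visit 5 to 6: 28 ± 7 days each (9.3, 9.5.1).
- Early termination visit: day 0 to 30 after ending treatment (9.6).
- DLT and stopping windows: 30 days (8.5, 11.4).
- Removal after a related-AE delay of more than 6 weeks (42 days) from the planned dose date (8.3).

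**1. Visit and windows counted from the same date.** Unobserved days = 30 − D, where D is the day of the termination visit.

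| D | 0 | 7 | 14 | 21 | 28 | 30 |
|---|---|---|---|---|---|---|
| Unobserved days | 30 | 23 | 16 | 9 | 2 | 0 |

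This holds whether the common date is the last dose or the decision to stop.

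**2. A path under the protocol's own rules.** A subject with one injected lesion progresses at Visits 2 and 3 and is withdrawn at Visit 3 under Table 7. The last dose was at Visit 2. If the termination procedures are done the same day, they fall 14 ± 3 = 11 to 17 days after that dose. Unobserved: 30 − 17 = 13 to 30 − 11 = 19 days.

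**3. Windows counted from the last dose, 9.6 counted from a decision at the next planned visit.**

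- Last dose at Visit 1: termination visit from 21 − 3 = 18 to 21 + 3 + 30 = 54 days after the dose.
- Last dose at Visit 2 or 3: from 14 − 3 = 11 to 14 + 3 + 30 = 47 days after the dose.

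The visit may therefore come before or after day 30.

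**4. Six-week delay rule.** Nominally, removal comes more than 21 + 42 = 63 days after a last dose at Visit 1, or more than 14 + 42 = 56 days after one at Visit 2 or 3. Taking 3 days off for the visit window gives 60 and 53. A window counted from the last dose has already closed.

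**5. Completers.** Visit 5 falls 21 to 35 days after Visit 4, so it may come before day 30. Visit 6 falls from 21 + 21 = 42 to 35 + 35 = 70 days after Visit 4. An AE assessment after day 30 is always scheduled.

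**The case against.** The strongest reply is that the documents do not establish an early exit.

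- **9.8 and Section 15.** Section 9.8 names follow-up visits alongside early termination, so it can be read as keeping early stoppers in follow-up. Section 9.5 says what completers do; it does not bar others. Section 15 lets a subject who stops the product go on with assessments. This stands in part: the gap is possible, not certain. But continuation under Section 15 is the subject's choice, that sentence concerns subjects who wish to stop, and nothing expressly requires a later contact.
- **Undefined clock.** The three sections use different phrases for the end of treatment and tie none of them to the last injection. This stands, and is part of the defect. Under step 3 the visit may come late enough; under step 1 it need not.
- **DLT stoppers.** A subject removed under the six-week rule is past day 30 from the last dose. This stands for that route. Other routes, such as ongoing antiviral treatment (8.5), persistent discomfort (11.4) or Table 7, can be earlier.
- **DLT incidence is not an endpoint.** This is correct, and a DLT that first appears after permanent discontinuation changes no dosing for that subject. AE and SAE incidence and the stopping criteria are still affected.
- **Other reporting channels.** SAEs and deaths are reportable within 24 hours of notification with no stated cut-off (11.5), and suspected herpetic events within 24 hours of awareness (13.2). These matter, but they are passive and elicit nothing. The four-weekly AE review in 11.2 follows the assessment schedule, which shows nothing after the termination visit for a subject not in follow-up.

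**Conclusion.** As written, the plan allows the last required AE assessment of an early stopper to fall before the 30-day windows in 8.5 and 11.4 close. The shortfall is 0 to 30 days when visit and window share a starting date. It is 13 to 19 days in the Visit 2 to Visit 3 example, which assumes that the termination visit is held on the day of withdrawal. Completers have no such gap.

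A reader might infer more than the documents support:

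- That early stoppers do leave before the windows close. They can; whether they do depends on the visit day, on how 9.8 and Section 15 are applied, and on the reason for stopping.
- That half the window is lost on average. This needs an assumed uniform spread of visit days, for which the documents give no basis.
- That early stoppers are the likeliest to have late related events, so that AE incidence is undercounted. No figure in the documents shows this, and no dropout rate is given.

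How a subject without a Visit 6 response assessment counts in the efficacy analysis is a separate question. The sample size and decision rule do not depend on this point. The change is worth making because it is cheap and bears on safety capture.

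**What to change.** 1. **In 9.6**, state that the early termination AE assessment is complete only when made on or after day 30 from the last injection. Either re-time the existing visit, or keep an earlier visit and add a telephone AE check on or after day 30. If the visit is re-timed, its present upper limit must be reworded: counted from the last injection, the two conditions meet on day 30 alone.
2. **In 8.5 and 11.4**, start the 30-day windows from that same date, so that the assessment and the windows share one clock.
3. **Reconcile 9.5, 9.8, Section 15 and Table 7** on whether subjects who stop injections without withdrawing consent continue to Visits 5 to 8. A blanket requirement that they do would collide with the Table 7 withdrawal rule, so the sponsor should settle which passage governs.

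The cost is a short amendment across these sections, and one later visit or one call for each early stopper affected. With it, unobserved days fall from a possible 0 to 30 to none for every subject who can be reached. No dose or treatment rule changes.
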